## Glossary of terms

Assessment	A procedure used to generate data required by the study
End of Study Visit	Point/time at which the patient came in for a final evaluation visit or when study drug was discontinued whichever is later
Enrollment	Point/time of patient entry into the study at which informed consent must be obtained (i.e. prior to starting any of the procedures described in the protocol)
ETDRS - standards	Early Treatment Diabetic Retinopathy Study-standards became the standard for all subsequent ophthalmological clinical trials; they include specific guidelines and requirements on how BCVA is being assessed and the equipment to be used for this assessment
Fellow treated eye	The fellow eye treated with ranibizumab
Patient withdrawal	Point/time when the patient exits from the study before the planned completion of all study drug administration and assessments; at this time all study drug administration is discontinued and no further assessments are planned
Period	A minor subdivision of the study timeline; divides phases into smaller functional segments such as Screening, Baseline, Monthly treatment, and PRN treatment
Protocol	A written account of all the procedures to be followed in a trial, which describes all the administrative, documentation, analytical and clinical processes used in the trial.
Study drug	A drug administered to the patient as part of the required study procedures; includes investigational drug, active drug run-ins or background therapy
Study eye	The study eye is the eye selected by the Investigator at Baseline (according to the protocol) to receive the study treatment
Subject number	A number assigned to each patient who enrolls in the study. When combined with the center number, a unique identifier is created for each patient in the study
Variable	A measured value or assessed response that is determined in specific assessments and used in data analysis to evaluate the drug being tested in the study

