Secondary Objectives	
To evaluate whether treatment with intravitreal ranibizumab is associated with improvements in various retinal morphology parameters as determined by SD/HD-OCT at various time points over a period of 6 months and evaluated by the Central Reading Centre (CRC) including:
 
 
• The change in subfoveal retinal thickness (SRT), central subfield retinal thickness (CSRT) and central subfield retinal volume (CSRV).
 
• The proportion of patients with subretinal fluid (SF), intra-retinal cystoid changes (IRC), pigment epithelial detachments (PEDs),
 

	
or dry retina.
 
 
The change in size (height or volume as appropriate) of various anatomical parameters including SF, IRC, and PEDs.
 
 
To evaluate changes from Baseline BCVA at various time points over a period of 6 months including changes in BCVA between 3 and 6 months.
 
To evaluate ocular and systemic safety by determining the incidence of ocular and systemic adverse events (AEs) up to Day 180.

Study design
	
This is a 6-month, phase IV, unmasked, uncontrolled, single arm, multicenter study. The study includes 8 study visits over a minimum of 6 months. All patients with nAMD and eligible to enter the study will receive 3 monthly intravitreal (IVT) ranibizumab 0.5mg injections followed thereafter by monthly IVT injections of ranibizumab 0.5mg on a PRN basis.

Population
	
The study will include 124 patients diagnosed with visual impairment due to nAMD who have been treated with aflibercept and where either no treatment response has been achieved or where there is suboptimal treatment response.

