## **4 Population**

The study will include patients diagnosed with visual impairment due to nAMD who have been treated with aflibercept and where either no treatment response has been achieved or where there is suboptimal treatment response. Assuming an approximate 20% screen failure rate, approximately 155 patients will need to be screened to have 124 eligible patients commencing treatment in the trial. Approximately 40 ophthalmology centers in Western European countries will be initiated.

It is anticipated that patients with primary treatment failure to aflibercept (see Section 4.1 for definition) are likely to achieve small responses to treatment with ranibizumab. In order to minimize potential risks to these patients, a maximum of 30 patients will be recruited in this subgroup.

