### **5.3 Treatment assignment, randomization**

This is not a randomized study. Patients will meet eligibility criteria for either the primary treatment failure subgroup or the secondary suboptimal response subgroup (see Section 4.1). Recruitment of patients into the primary treatment failure subgroup will be up to a maximum of 30 patients. Recruitment to this subgroup will be closed once this number of patients has been allocated to the primary treatment failure subgroup, and have both successfully completed the Screening assessments and confirmation of eligibility has been entered into the eCRF.

At the Baseline Visit (Day 1), all eligible patients will receive IVT injection of ranibizumab 0.5mg into the study eye. Repeat ranibizumab injections will only occur at scheduled study visits; i.e. at Day 30 ( $\pm 7$ ) and Day 60 ( $\pm 7$ ). Repeated ranibizumab injections may also occur according to the protocol defined re-treatment criteria (see Section 5.5.4) at Day 90 ( $\pm 7$ ) and Day 120 ( $\pm 7$ ). After each visit has been performed the eCRF needs to be updated with the details of whether an injection has been administered or not.

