## **6.2 Patient demographics/other baseline characteristics**

Patient demographic and baseline characteristics to be collected on screened patients include:

- Demography: year of birth, gender, race, ethnicity
- Relevant medical history/current medical condition data includes data until the informed consent form is signed. Where possible, diagnoses and not symptoms will be recorded. Investigators will have the discretion to record abnormal test findings on the medical history eCRF whenever the test abnormality occurred before the informed consent signature
- Study eye selection
- Baseline characteristics
- Prior utilization of aflibercept (number and dates of injections into one or both eyes)
- Other assessments performed at Screening to determine eligibility are listed in Table 6-1.

At the Baseline visit and after review of eligibility criteria, patients will be allocated to either the primary treatment failure subgroup or to the suboptimal treatment response subgroup.

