Data will be analyzed by [REDACTED] according to the data analysis section 9 of the study protocol which is available in Appendix 16.1.1 of the clinical study report (CSR). Important information is given in the following sections and details are provided, as applicable, in Appendix 16.1.9 of the CSR.

Following are the changes from the protocol planned analysis:

- [REDACTED]
- SF volume and IRC volume were mentioned in the protocol as secondary efficacy variables. Due to technical limitations, there is no robust way in the reading center to assess these two parameters. CSRT thickness and subfoveal retinal thickness will be used to assess SF volume, and maximum height of intra-retinal cysts (IRC) will be used to assess IRC volume.
- ‘Intra-retinal cystoid changes’ was listed as a variable in the secondary objectives section. This is being assessed by presence of intraretinal fluid and whether some of the intraretinal fluid is of cystoid origin.
- [REDACTED]

This is a phase IV, unmasked, uncontrolled, single arm, and multicenter study in patients diagnosed with visual impairment due to nAMD who have been treated with aflibercept and where either no treatment response has been achieved or where there is suboptimal treatment response. The study will enroll 150 patients in 30 ophthalmology centers in Western European countries. Patients will be enrolled according to 2 subgroups: primary treatment failure subgroup (maximum of 30 patients) or suboptimal response subgroup.

The study includes 8 study visits over a minimum of 6 months. All patients with nAMD and eligible to enter the study will receive 3 monthly intravitreal (IVT) ranibizumab 0.5mg injections followed thereafter by monthly IVT injections of ranibizumab 0.5mg on a pro re nata/administer as required (PRN) basis. There will be 3 periods in this study: Screening period from Day -70 to Day 0, Monthly Treatment period from Baseline (Day 1) to Day 60, and PRN Treatment period from Day 61 to Day 180.

All assessments will be performed according to the assessment schedule (see Table 6-1 and Table 6-2 in Section 6 of the protocol).

The purpose of this study is to determine, in patients with nAMD treated with aflibercept and where there is evidence of persistent or increasing disease activity, whether switching treatment to ranibizumab 0.5mg reduces disease activity over a 6 month period as assessed by a variety of measures.

2 Statistical and analytical plans

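### Does the SAP's figure of 150 patients in 30 centres contradict the protocol's plan of 124 treated patients?

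*SAP*

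**What the plan says.** The SAP gives its planned size once, in the study description that precedes its Section 2: "The study will enroll 150 patients in 30 ophthalmology centers in Western European countries". The next sentence adds: "Patients will be enrolled according to 2 subgroups: primary treatment failure subgroup (maximum of 30 patients) or suboptimal response subgroup".

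The protocol's figures are different. The Protocol summary says: "The study will include 124 patients diagnosed with visual impairment due to nAMD". Section 4 (Population) assumes a screen failure rate of roughly 20% and states that "approximately 155 patients will need to be screened to have 124 eligible patients commencing treatment in the trial". On sites it says: "Approximately 40 ophthalmology centers in Western European countries will be initiated".

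Two further places bear on what the SAP's verb means. The protocol's Glossary of terms defines enrolment as "Point/time of patient entry into the study at which informed consent must be obtained". Section 5.5.1 fits that definition, because a subject number is issued when consent is signed and the glossary gives a subject number to each patient who enrols. The subgroups come later. Section 5.3 closes the capped group once 30 patients have been allocated to it and have "successfully completed the Screening assessments and confirmation of eligibility has been entered into the eCRF". Section 6.2 says that at the Baseline visit, "after review of eligibility criteria, patients will be allocated to either the primary treatment failure subgroup or to the suboptimal treatment response subgroup".

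**The concern.** A reader who checks one document against the other finds 150 against 124 patients and 30 against 40 centres. Version timing does not explain it: Amendment 2 moved the protocol from 162 treated and 200 screened to 124 and 155, and 150 is none of these four numbers. Replacement of withdrawals does not explain it either, since Section 5.5.9 rules that out.

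The planned number matters when disposition is reported. Section 5.5.13 stops entry to treatment once that number has been found eligible, and Section 11.1 allows changes to the protocol only by written amendment. If 150 were a second, larger target for treated patients, a trial that treated between 124 and 149 would meet the protocol and miss the SAP. A real change of target would then lack a visible amendment.

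**Working it through.** **Inputs.** SAP study description: 150 patients, 30 centres, cap of 30 in the primary treatment failure group. Protocol Section 4: 124 treated, about 155 screened, about 20% screen failure, about 40 centres initiated. Amendment 2: SD of differences cut from 117 to 102 µm, sample size cut from 162 to 124.

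**1. Is the protocol consistent with itself?**
- Number to screen = treated / (1 − failure rate) = 124 / 0.80 = 155. This reproduces the stated figure exactly.
- Scaling the former sample size by the variance ratio gives 162 × (102/117)² = 123.1, in line with 124.

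The protocol's arithmetic holds, so the SAP sentence is the outlier.

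**2. Reading A: 150 counts consented patients (the glossary's definition).**
- Gap from the screening figure: 155 − 150 = 5, and 5/155 = 3.2%.
- Treated at 20% screen failure: 150 × 0.80 = 120, which is 4 short of 124.
- Screen failure rate at which 150 gives 124: 1 − 124/150 = 17.3%.

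Both protocol quantities, 155 and 20%, are stated as approximate. A round 150 fits them.

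**3. Reading B: 150 counts treated patients.**
- Excess: 150 − 124 = 26, and 26/124 = 21.0%.
- Screening needed: 150 / 0.80 = 187.5, so about 188.
- If the cap of 30 were filled, suboptimal responders would number 150 − 30 = 120, against 124 − 30 = 94.

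This is the only reading with a material gap.

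**4. Which reading does the text support?** Reading B rests on the SAP's next sentence, which ties enrolment to subgroups that the protocol assigns to eligible patients. But SAP Section 2.1.2 tabulates disposition by subgroup and overall, and the first row of that table is patients screened. The SAP therefore attaches a subgroup to screened patients too, which weakens the inference. Several subgroup criteria in protocol Section 4.1 are also anchored to the Screening Visit. Reading A has an explicit definition behind it.

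**5. Centres.** 30/40 = 75%. The protocol counts sites to be initiated; the SAP speaks of sites in which patients enrol. An initiated site need not enrol anyone, so these are not necessarily the same count.

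**6. Does anything depend on 150?** The analysis sets (SAP Section 2.1.1) are defined by treatment received and assessments available. The interim analysis (Section 2.5) is triggered by 50 patients reaching Day 90. The primary summary (Section 2.2.1.2) uses whoever is in the full analysis set. None of them refers to 150 or to the number of centres.

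For scale, take Amendment 2's SD of 102 µm and a normal approximation. The 95% half-width for the mean change, 1.96 × 102/√n, is then:

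| Patients analysed | Half-width (µm) |
|---|---|
| 120 | 18.3 |
| 124 | 18.0 |
| 150 | 16.3 |

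Even the widest disagreement between readings moves precision by less than 2 µm.

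**The case for a change.** The best case for a change is that it is cheap and the ambiguity is real. The SAP never says whether its number means consented or treated patients. Its disposition table has rows for screened and for treated at V2, but none for enrolled, so it is unclear which row 150 should be checked against. The cap restated in the next sentence does apply, in the protocol, to patients already confirmed eligible. The visible entries in the SAP's list of changes from the protocol concern OCT variables only, and one sentence of rewording would settle the matter.

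Much of this stands: the figures differ, and the wording could be clearer. It does not show that the SAP sets a second target for treated patients. Repeating the cap beside 150 does not define 150. Two entries in the list of changes are redacted and protocol Section 9.7 is not in the public text, so an explanation cannot be excluded. Overwriting the SAP with the protocol's figures could also do harm: if 30 is the number of enrolling centres, replacing it with 40 would remove a correct figure. The reporting risk is slight as well, because the SAP defers to protocol Section 9 for the analysis, and Amendment 2 places the sample size of 124 in Section 9.7.

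**Conclusion.** The inconsistency is genuine but clerical. On the protocol's own definition of enrolment, the patient figures differ by 5 in about 155 (3.2%), within the looseness of two approximate planning values. The 26-patient gap (21.0%) needs a reading that the text does not establish. The centre counts may measure different things.

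Neither document contains a wrong calculation. The SAP sentence describes the study and drives nothing: no analysis set, estimate, test, interim trigger or recruitment rule in the public text uses it. The protocol controls entry to treatment and can change only by amendment. An analyst reporting disposition would take 124 from the protocol as the planned number treated and use the SAP's own screened and treated-at-V2 counts. Rewording the sentence would alter no analysis, result or conclusion, so no change to the plan is called for.

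This rests on two assumptions: that the glossary's meaning of enrolment carries over to the SAP, and that the redacted text holds no analysis that depends on 150.

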2.1 Patients and treatments

2.1.1 Analysis sets

Assignment of patients to analysis sets will be agreed between the study statistician and the Sponsor prior to database lock, once all study data are available and verified. All efficacy analyses will be performed on the study eye. For visual acuity tests, the results for the fellow eye (non-study eye) will also be summarized for reference.

Full Analysis Set (FAS): The FAS consists of all patients who received at least one application of study treatment in the study eye, have baseline and have at least one post-baseline assessment for CSRT. Following the intent-to-treat principle, patients will be analyzed according to the treatment assigned. No data will be excluded from the FAS analyses because of protocol deviations.

Per Protocol Set (PPS): The PPS consists of all patients in the FAS who followed the assigned treatment and completed the study without clinically significant protocol deviations.

Safety Set (SAF): The SAF consists of all patients who received at least one application of study treatment in the study eye and had at least one post-baseline safety assessment.

All efficacy evaluations will be carried out on the Full Analysis Set and all safety evaluations will be carried out on the Safety Set. For sensitivity purposes, the primary analysis will be repeated using the Per Protocol Set. Any major discrepancies in the results across analyses will be investigated as necessary.

In addition, 2 subgroups of patients are defined:

- Group 1. Primary treatment failure (PTF)
- Group 2. Suboptimal treatment response (STR)

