### **5.5.7 Concomitant treatment**

The Investigator should instruct the patient to notify the study site about any new medications he/she takes after the patient was enrolled into the study. All medications (including for non-ophthalmic conditions), procedures and significant non-drug therapies (including physical therapy and blood transfusions) administered after the patient was enrolled into the study must be recorded in the eCRF.

Medications that may be used as part of the protocol specified retinal image acquisition (e.g., mydriatic drops, fluorescein dyes) and pre- and post-injection medications (e.g., topical anesthetics, topical antimicrobials) used by a patient during the study, are not considered concomitant medications.

If a patient requires intraocular surgery on the study eye during the course of the study, the patient should be withdrawn from the study.

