**Table 5-1 Prohibited treatment**

Medication	Action to be taken
Anti-VEGF drugs other than ranibizumab (ocular or systemic)	Withdraw patient from study
Intra- or periocular corticosteroids (including sub-tenon but excluding topical formulations) – study eye only	Withdraw patient from study
Intra-ocular corticosteroid implants – study eye only	Withdraw patient from study
Investigational drugs and interventions of any type	Withdraw patient from study

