### 5.5.9 Discontinuation of study treatment

Patients may voluntarily discontinue study treatment for any reason at any time.

The study and treatment completion dates will be determined by the last visit the patient came to the clinic.

The Investigator must provide follow-up medical care for all patients who are prematurely withdrawn from the study, or must refer them for appropriate ongoing care. Patients who are prematurely withdrawn from the study will not be replaced by an equal number of newly enrolled patients.

Patients can discontinue study treatment because of the appearance of a new health condition suspected to require appropriate care or require medications prohibited by the protocol (Section 5.5.8), unacceptable AEs, refusal to continue treatment, or at the Investigator's discretion based on his or her clinical judgment.

The Investigator should discontinue study treatment for a given patient or withdraw the patient from study if, on balance, he/she believes that continuation would be detrimental to the patient's well-being.

Study treatment must be discontinued under the following circumstances:

- Withdrawal of informed consent
- Emergence of the following AEs:
  - Stage 3 or 4 macular hole
  - Stroke or transient ischemic attack
  - Rhegmatogenous retinal detachment
- Pregnancy
- Use of prohibited treatment in Table 5-1
- Two sequential ranibizumab injections to the study eye should have occurred according to the protocol specified monthly/PRN treatment period criteria but were withheld (see Section 5.5.5) or missed.

- Any other protocol deviation that results in a significant risk to the patient's safety.

Patients who permanently discontinue study treatment and start a prohibited non-study treatment (see Section 5.5.8) should be withdrawn from the study and undergo all assessments for End of Study visit as described in Table 6-1 and Table 6-2.

Patients who discontinue study treatment but do not receive prohibited treatment should not be considered withdrawn from the study and may continue their scheduled follow-up assessments until End of Study.

The Completion/Withdrawal eCRF page should be completed, providing the primary reason for stopping study treatment.

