### **5.5.13 Study completion and post-study treatment**

Patients who already have entered the Screening Period should not enter the Treatment Period once the planned number of patients has been found eligible to commence treatment in the study.

The Investigator must provide follow-up medical care for all patients who are prematurely withdrawn from the study, or must refer them for appropriate ongoing care.

Patients who successfully complete all study assessments of the study through to Day 180 will be considered to have completed the study.

The study is considered as completed once, according to the study protocol, all protocol required activities have been executed in all treated patients.

No extension study has been planned.

Following completion of the study, all patients will be provided with appropriate ongoing care according to the Investigator's or treating ophthalmologist's judgment.

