### 9.1 Analysis sets

For all patients only one eye will be considered as the study eye, but efficacy and safety parameters will be recorded for both eyes. In the event that a subject develops visual impairment due to nAMD in the fellow eye (non-study eye) during the study which is treated at the Investigator's discretion according to the standard of care, any additional data (except for BCVA, ranibizumab injections and AEs and SAEs that occur in the fellow eye) collected according to routine practice will not be recorded on the eCRF. Data presentations will distinguish study and fellow eye values.

The **Full Analysis Set (FAS)** will consist of all patients who received at least one application of study treatment in the study eye, have baseline and have at least one post-baseline assessment for CSRT. Following the intent-to-treat principle, patients will be analyzed according to the treatment assigned. No data will be excluded from the FAS analyses because of protocol deviations.

The **Per Protocol Set (PPS)** will consist of all patients in the FAS who followed the assigned treatment and completed the study without clinically significant protocol deviations. Clinically significant protocol deviations will be defined in the Statistical Analysis Plan. If deviations do occur, then the data from specific patients, visits, or evaluations may be excluded from the PPS. The criteria and determination of clinically relevant protocol deviations and patient specific identification of data to be excluded from the PPS will be databased and finalized prior to database lock.

The **Safety Set (SAF)** will consist of all patients who received at least one application of study treatment in the study eye and had at least one post-baseline safety assessment. The statement that a patient had no adverse events also constitutes a safety assessment.

All efficacy evaluations will be carried out on the Full Analysis Set and all safety evaluations will be carried out on the Safety Set.

For sensitivity purposes, the primary analysis will be repeated using the Per Protocol Set. Any major discrepancies in the results across analyses will be investigated as necessary.

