#### **9.4.4 Supportive analyses**

For sensitivity purposes, the primary analysis will be repeated using the PPS. Any major discrepancies in the results across analyses will be investigated as necessary. For the PPS, it is assumed that a complete set of valid observations for the efficacy endpoints will be available. Therefore, no general rules for handling of missing values are specified. In case missing values occur, details regarding their handling will be described in a Statistical Analysis Plan.

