2.2.1.2 Descriptive analyses

The change in CSRT from baseline to Day 90 will be summarized together with the 95% CI for the mean and absolute values of CSRT at baseline and at Day 90.

In the event that CSRT is missing for Day 90, the analysis will follow an LOCF (Last Observation Carried Forward) approach for the FAS.

The primary analysis will be performed on the FAS.

For sensitivity purposes, the primary analysis will be repeated using the PPS.

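### The Per Protocol Set requires completion to Day 180 but is used only to repeat the Day 90 analysis, so patients with a valid Day 90 CSRT can be dropped for leaving later

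*SAP*

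**What the plan says.** SAP 2.1.1 defines the set: "The PPS consists of all patients in the FAS who followed the assigned treatment and completed the study without clinically significant protocol deviations". Protocol 9.1 uses the same wording. Completion has a stated meaning in Protocol 5.5.13: "Patients who successfully complete all study assessments of the study through to Day 180 will be considered to have completed the study".

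The use of the set is narrow. SAP 2.2.1.2 says: "For sensitivity purposes, the primary analysis will be repeated using the PPS". Protocol 9.1 and 9.4.4 and SAP 2.1.1 say the same. The primary variable is the change in CSRT from baseline to Day 90 (Protocol 9.4.1, SAP 2.2.1.1). Secondary efficacy is assigned to the FAS (Protocol 9.5.1, SAP 2.2.2.2).

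Three other provisions bear on who stays in the set:

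- Protocol 9.4.4: "For the PPS, it is assumed that a complete set of valid observations for the efficacy endpoints will be available". It then leaves the handling of any missing values to the SAP.
- Protocol 9.1 allows particular visits or evaluations, and not only whole patients, to be left out because of deviations.
- SAP 2.1.3 gives deviation codes. Code 1 removes the patient from the PPS. Code 2 removes data from the deviation date onward and keeps the patient.

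**The concern.** Membership of the set depends on events up to three months after the measurement it is used to analyse. Visits at Days 120, 150 and 180 follow the Day 90 OCT, and nothing that happens at or between them can change the Day 90 value.

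At least one exit route may relate to response. Protocol 5.5.9 says: "Patients who permanently discontinue study treatment and start a prohibited non-study treatment (see Section 5.5.8) should be withdrawn from the study". Table 5-1 counts any anti-VEGF drug other than ranibizumab as prohibited, so a patient who did poorly by Day 90 and moves to another agent leaves the study and, with it, the PPS. Other routes need not relate to response: loss to follow-up, systemic or fellow-eye anti-VEGF treatment, or study-eye surgery, on which Protocol 5.5.7 says: "If a patient requires intraocular surgery on the study eye during the course of the study, the patient should be withdrawn from the study".

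The rules are also not reconciled. The completion condition and the complete-data assumption in Protocol 9.4.4 point to a completers-only set. Visit-level exclusion and code 2 point to a set that keeps a patient's earlier data. The documents do not say which applies to a patient with a code 2 deviation who does not complete.

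At stake is how to read the only sensitivity analysis of the primary endpoint in the available text. As defined, a difference between FAS and PPS mixes conduct up to Day 90 with attrition after it.

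**Working it through.** **Logic**

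1. PPS membership requires completing the study (SAP 2.1.1, Protocol 9.1).
2. Completing means all assessments through Day 180 (Protocol 5.5.13).
3. The PPS analysis uses CSRT at baseline and Day 90 only (SAP 2.2.1.1, 2.2.1.2).
4. So a patient observed at Day 90 who leaves before Day 180 has everything the analysis needs and is still excluded.

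**Size**

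The plan gives no figure to reproduce here and no attrition rate, so this is a range under stated assumptions.

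Inputs from the documents:
- SD of the change: 102 µm (Protocol, History of Amendments, Amendment 2).
- Patients: n = 124 (Protocol 4) or 150 (SAP introduction).

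Assumptions:
- 5%, 10% or 15% leave after Day 90. Rounded, k = 6, 12, 19 for n = 124 and k = 8, 15, 23 for n = 150.
- The share p of leavers from the worse half of Day 90 changes is 0.5 (1:1), 0.6 (1.5:1) or 2/3 (2:1).
- Changes are normally distributed, and there are no other PPS exclusions.

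For a normal variable, the mean of the worse half lies SD × √(2/π) above the overall mean: 102 × 0.798 = 81.4 µm. Leavers therefore differ from the overall mean by (2p − 1) × 81.4 µm, which is 0, 16.3 or 27.1 µm. Removing k of n patients moves the mean of those who remain toward a larger reduction by

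shift = k(2p − 1) × 81.4 / (n − k).

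Example: n = 124, k = 19, p = 2/3 gives 19 × (1/3) × 81.4 / 105 = 4.91 µm.

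The 95% CI half-width is t(0.975, n − k − 1) × 102 / √(n − k).

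| n | k | n − k | Shift at 1:1 (µm) | Shift at 1.5:1 (µm) | Shift at 2:1 (µm) | CI half-width (µm) |
|---|---|---|---|---|---|---|
| 124 | 6 | 118 | 0 | 0.83 | 1.38 | 18.6 |
| 124 | 12 | 112 | 0 | 1.74 | 2.91 | 19.1 |
| 124 | 19 | 105 | 0 | 2.95 | 4.91 | 19.7 |
| 150 | 8 | 142 | 0 | 0.92 | 1.53 | 16.9 |
| 150 | 15 | 135 | 0 | 1.81 | 3.01 | 17.4 |
| 150 | 23 | 127 | 0 | 2.95 | 4.91 | 17.9 |

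The largest shift relative to the half-width is 4.91/19.7 = 0.25 (n = 124) or 4.91/17.9 = 0.27 (n = 150). A simulation with 40,000 runs per cell agreed with the formula to within about 0.1 µm. The shift does not depend on the true mean change and is proportional to the SD.

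The precision cost is small: with n = 124 the half-width is 18.1 µm with no late loss and 18.6 to 19.7 µm at 5% to 15%.

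**The case against.** The strongest reply is that the response-related route may already be covered. Starting another anti-VEGF drug appears to be a protocol deviation, and deviations are classified by the codes in SAP 2.1.3. Under code 2 the Day 90 value would be kept; under code 1 the patient is out whatever completion means. The assignment is in VAP Module 3 (SAP Appendix 2), whose content is not in the text available. This stands in part: how much bias comes from the completion wording alone depends on that list. But the codes govern deviations. They do not lift the separate completion condition, and nothing available keeps in the PPS a patient who simply withdraws or is lost after Day 90.

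Other points stand as limits on importance. PRN ranibizumab remains available from Day 90 to Day 150, and stopping study treatment without prohibited therapy is not withdrawal (Protocol 5.5.9), so response-related exits may be few. The attrition rates and splits above are assumed. Analysis sets are agreed before lock, exclusion reasons are listed and discrepancies are to be investigated (SAP 2.1.1, 2.1.2), so the effect could be traced afterwards. Protocol 9.4.4 also provides for missing values in the PPS, which weakens it as evidence for a strict completers-only reading.

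One could defend a whole-study PPS as a deliberately strict set in a study that Protocol 3.2 calls exploratory. That would be more persuasive if the set served any analysis beyond Day 90; in the text available it does not.

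**Conclusion.** The concern holds on the text available. The PPS conditions a Day 90 analysis on staying in the study to Day 180, and the deviation rules do not resolve the conflict. It should be corrected, but its reach is limited: the FAS primary analysis keeps these patients, and only the supportive repeat is affected.

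Bias is possible, not established. It arises only if leaving after Day 90 relates to response, and its direction is toward a larger reduction only if poorer responders leave more often. Under the assumptions above it ranges from 0 to 4.9 µm, at most about a quarter of the CI half-width. If leaving is unrelated to response, the cost is the loss of valid Day 90 values: 6 to 19 of 124, or 8 to 23 of 150, at the assumed rates. That the PPS has no other use is a statement about the text available.

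**What to change.** For the repeat of the primary analysis, define the PPS in SAP 2.1.1 as FAS patients who followed the monthly-period treatment, have an observed Day 90 CSRT, and had no clinically significant deviation before the Day 90 OCT. Remove the completion-to-Day-180 condition and state that code 2 deviations dated after that OCT leave the Day 90 value in the analysis. Use the OCT, not the visit, as the cut-off, because Protocol 6.4 places efficacy assessments before any injection at the same visit. Add one conditional sentence to SAP 2.1.3: if VAP Module 3 gives code 1 to a deviation that can first occur after the Day 90 OCT, that deviation does not remove the Day 90 value.

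The cost is wording, settled before database lock. No new data are needed and the FAS primary analysis does not change. Protocol 9.1 should carry matching text. A protocol edit needs a formal amendment under Protocol 11.1, but the SAP already opens with a list of changes from the protocol's planned analysis, so the change can be recorded there.
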